2.2.1.2 Efficacy of Sodium Hyaluronate

HA is a polymer with distinctive viscoelastic and hygroscopic properties that has demonstrated its therapeutic effect in patients with SOS. As an active ingredient, HA has shown an increase in the quality of life and satisfaction level (44.5% – 70.2%) of patients with SOS after 7 days of treatment. [26]

Saeed et al. studied the efficacy, safety, and tolerability of HA in 240 patients treated with a 0.4% HA ophthalmic solution. After 8 weeks of treatment, ocular signs and symptoms decreased compared to baseline, reporting a 5.3% difference in foreign body sensation (SCS) and pruritus. Similarly, Pito-Fraga

et al. reported a significant increase in patient satisfaction with mild SOS after being part of a one-month crossover study with 0.2% HA compared to 0.9% saline (26.8% vs 13.3%). [26]

Aragona et al. also described the efficacy of HS in patients with SOS who, after 3 months of treatment, showed improvement in the results of impression cytology. They concluded that long-term treatment with artificial tears containing HS reduces ocular surface damage in patients with SOS. [27]

Combinations of lubricants such as 0.1% HA with 0.5% carboxymethylcellulose have also been studied, finding this formulation effective in reducing SOS symptoms in patients recovering from cataract surgery, as evidenced by the OSDI questionnaire. [26]

HS, like other viscous materials, has been shown to have greater effects than other conventional aqueous artificial tears on decreased fluorescein uptake in patients with SOS.

These additional effects have been attributed to both the prolonged retention time and the physiological activity of HS. In a study published by Shimmura et al. comparing a 0.3% HS preservative-free solution with a non-viscous saline solution, it was observed that the HS formulation was more effective in reducing fluorescein staining in patients with SOS. [13]

2.2.1.3 Safety of Sodium Hyaluronate

2.2.1.3.1 Preclinical studies

Several studies of the safety of HA have been conducted. No toxicity has been observed in single-dose, repeated-dose, reproductive or developmental toxicity, mutagenicity, and antigenicity studies. [24]

In a study performed on a human conjunctival cell line by cytofluorometry with cold light microtitration to evaluate cellular tolerance to HS and look for a protective action *in vitro*. Various cellular functions such as cell viability, cell proliferation, and the production of reactive oxygen species were evaluated. 0.18% HA was used. The tests were carried out after 15 minutes of treatment and after 24 hours of recovery of the cells in the culture medium. Ocular viability was assessed by a neutral red fluorimetry test. Chromatin condensation was assessed by measuring total cellular DNA as a reference in the assessment of apoptosis. Each test was performed at least three times. No decrease in cell viability was observed with HA, nor any change in membrane integrity after 24 hours. [28]

For the evaluation of single-dose toxicity, >1200 mg/kg HA has been administered orally to mice. In addition, the toxicity of acute and chronic HA administered by different routes such as inhalation in Beagle dogs, implantation in the paravertebral muscles of rabbits, peritoneal administration in albino rabbits New Zealand and pleural administration in white rats has been evaluated. All the studies mentioned supported the safety of HA. [29]

It was reported that after vitreous humour supplanting in *rhesus* monkeys and owl monkeys, when assessing inflammation by leukocyte count in the aqueous humour, no significant differences were observed. Only two eyes of the owl monkeys and two *rhesus* monkeys showed slight vitreous turbidity, a reaction that disappeared between 72 and 96 hours for all subjects. These same authors repeated the procedure up to 6 times in owl monkeys, concluding that repeated HS implantation did not cause

increased turbidity and flare, as well as any other immune response. Even after a follow-up period of up to 9 years, in subjects who received 2 to 4 HS injections, it was concluded that all eyes were completely normal, with no alterations in the anterior segment, lens, vitreous, retina or choroid. [29]

With respect to dermal irritation, it was shown that HA does not cause alterations after a single dose in Japanese rabbits and Hartley guinea pigs. The ototoxicity of HA was also evaluated in pigmented Sprague-Dawley rats, concluding that the administration of this compound in the middle ear does not cause alterations to the auditory system. [29]

The reproductive and developmental toxicity of HS has been studied in preclinical studies *in vivo*. In a multigenerational study in Sprague-Dawley rats and in another conducted in Japanese white rabbits, HA solutions were administered subcutaneously at three different concentrations. Weights and feed intake, as well as the pathology of intraperitoneal organs and skeletal system after the sacrifice of the selected mothers and calves, were analyzed, without finding significant differences. There were also no differences between the intervened subjects and the control subjects when assessing gestation time, number of offspring, sex ratio, live embryos and fetuses, and viable fetuses. [29]

2.2.1.3.2 Clinical Trials

Aragona et al. (2002) reported that no AEs were present during a clinical study of efficacy and safety, after three months of treatment, in addition to good tolerability to the formulation. [27]

The immunogenicity of HS has been tested in humans, by allergy skin tests, without finding adverse reactions related to the compound. In addition, its safety has been reported when used in the treatment of vesicoureteral reflux and as an aid in tissue augmentation. [29]

2.2.2 Background on chondroitin sulfate

2.2.2.1 Pharmacology of chondroitin sulfate

Chondroitin sulfate is a proteoglycan, a class of high molecular weight glycoprotein that is highly glycosylated. It is an endogenous natural substance that is part of the physiological components of connective tissues, being one of the constituent elements of cartilage. It is part of the group of glycosaminoglycans, like sodium hyaluronate, it is a mucopolysaccharide found in the extracellular matrix of connective tissues, including the vitreous, cornea and aqueous humor. [25]

[figure not shown]

Figure 4. Chemical structure of CS

2.2.2.1.1 Pharmacokinetics in the eyeball

As for HS, there is currently no pharmacokinetic information following topical application of CS. However, due to its characteristics, particularly its high molecular weight, absorption by this route is not expected. To read more about this property and its interaction with the ocular surface epithelium, see section 2.2.1.1.1 Pharmacokinetics in the eyeball.

2.2.2.1.2 Systemic pharmacokinetics

CS, due to its high molecular weight, is partially absorbed in the intestine after being degraded to its polymeric form. The products of intestinal degradation are simple sugars, amino sugars and inorganic sulfate. Cueto-Galán et al. describe that the bioavailability of CS ranges from 15% to 24% of the orally administered dose. Of the absorbed fraction of CS, 10% is in the form of CS and 90% in the form of depolymerized derivatives of lower molecular weight, suggesting a first-pass effect. After oral administration of CS, the maximum concentration of CS in the blood is reached in about four hours.

In the case of intravenous administration, the plasma half-life of CS has been described as between 3-15 minutes, suggesting that the systemic effects of orally administered CS could be mediated by the intestinal immune system, including the gastrointestinal lymphoid system. The half-life of total CS is 15 hours, reaching a stationary period in 3-4 days. [25]

2.2.2.2 Efficacy of chondroitin sulfate

In 2013, Llamas-Moreno et al. published a clinical study sponsored by Laboratorios Sophia, S.A. de C.V. in which the efficacy and safety of a preservative-free ophthalmic solution containing chondroitin sulfate in combination with xanthan gum was evaluated, comparing it with a combination of polyethylene glycol/propylene glycol/hydroxypropyl guar. After two months of treatment in patients with mild to moderate SOS, it was reported that in both groups the TRL was similar, however, the OSDI test score showed a greater decrease in the chondroitin sulfate 0.09%/xanthan gum 0.1% group. [30]

The efficacy of this same combination was also studied in a phase III study published by Pérez-Balbuena, et al (2016). This was another comparative study in which it was compared with a solution of polyethylene glycol 400 0.4 % / propylene glycol 0.3 %. The variables studied in the 148 included patients with mild to moderate SOS were the TRL, OSDI test score, and Schirmer test. The results showed that both groups had similar clinical efficacy after two months of treatment. [31]

Limberg et al. (1987) published a clinical study in which 20 patients with keratoconjunctivitis sicca were treated with a viscoelastic formulation of chondroitin sulfate alone, another in combination with sodium hyaluronate, a third of sodium hyaluronate alone, and finally a polyvinyl alcohol solution. It was observed that treated patients showed marked improvement in terms of reduced pruritus, burning, and ECS severity. A reduction in corneal uptake and formation of mucosal filaments was also observed. It was reported that those patients who presented initial low results in the Schirmer test preferred the solution containing CS. [32]

2.2.2.3 Safety of Chondroitin Sulfate

In both studies previously mentioned in section 2.2.2.2 Efficacy of chondroitin sulfate published by Llamas-Moreno et al. (2013) and Pérez-Balbuena et al. (2016), the safety of the preservative-free ophthalmic solution composed of chondroitin sulfate 0.09%/xanthan gum 0.1% was analyzed by the incidence of ocular and systemic AEs during a period of 2 months of treatment. During this period, no AEs related to the intervention were presented in any of these studies, concluding that this formulation is safe. [30, 31]

2.3 Summary of pharmaceutical development of Humylub Ofteno® PF

Humylub Ofteno® PF has been developed at Laboratorios Sophia, S.A. de C.V. and has the physicochemical characterization and the protocol of accelerated and long-term stability.

In 2014, a preclinical safety and toxicity study was carried out in which Humylub Ofteno® PF was evaluated. This preservative-free formulation was compared with Humylub Ofteno®, after QID was applied for one month to the surface of both eyes of albino New Zealand rabbits. The primary variables evaluated were conjunctival hyperemia, corneal surface status, and histopathology toxicity data. Secondary endpoints included conjunctival secretion and other anterior segment alterations. During the execution of the study, only one subject with moderate hyperemia was presented, however, this finding was not statistically significant. In the same way, only one case of fluorescein staining was presented in the control group, without this being statistically relevant. The rest of the variables, including revision of the posterior pole, intraocular pressure, and staining with lysmine green, did not show alterations. Due to the results obtained, it was concluded that Humylub Ofteno® PF was safe, as was its comparator. [33]

Subsequently, a Phase I clinical study was conducted in which the safety and tolerability of Humylub Ofteno® PF was demonstrated compared to Xyel Ofteno® and Systane Ultra® products, on the ocular surface of ophthalmologically and clinically healthy subjects. As variables to evaluate tolerability, burning, ECS, pruritus, and ocular comfort index were analyzed. For the safety study, goblet cell density, presence of AEs, intraocular pressure, visual capacity, laboratory tests, epithelial defects in the cornea and conjunctiva, conjunctival hyperemia, and chemosis were considered. No statistically significant differences were observed between the density of initial goblet cells between the three treatments, nor in the final treatments. A total of 28 AEs were reported in 46.7% of the subjects in the total sample (14/30), of which 100% were classified as mild. For lysmine green staining, a statistically significant difference was observed at visit 2, while for fluorescein staining, statistically significant differences were observed at visits 1, 2, and final at the expense of a higher number of grade 0 cases in the comparator group. For conjunctival hyperemia, statistically significant differences were only observed at visit 1 where the group treated with

Systane Ultra® showed a higher frequency of normal values compared to Humylub Ofteno® PF and Xyel Ofteno®. No statistically significant differences were observed between the density of initial goblet cells between the three treatments, nor in the final treatments. In the variables evaluated, both safety and tolerability, Humylub Ofteno® PF showed a safety profile like that of the comparators, so it was concluded that it is a safe and tolerable formulation. [34]

Finally, in 2019, a multicenter phase IV study was carried out, in which the efficacy and safety of Humylub Ofteno® PF was evaluated compared to Systane® Ultra and Systane® Ultra free of preservatives. In this study, with a duration of 90 days, 326 patients were included. In efficacy variables, such as TRL, Schirmer's test, OSDI, and goblet cell density, all three treatment groups were effective, showing statistically significant improvement between their baseline and final visits. However, no group was consistently and statistically significantly superior to the other. For the variables defined as primary safety outcomes, such as presence of AEs, TRL, visual acuity and ability, intraocular pressure (IOP), and surface stains, no statistically significant differences were observed between groups in any of the measurement times. Finally, for the variables marked as tolerability (burning, SCE, tearing, and conjunctival hyperemia) there were no differences between groups; however, there was improvement in relation to the baseline visit. Based on the results presented above, it was concluded that Humylub Ofteno® PF is a safe and effective lubricant in the treatment of mild to moderate dry eye. [35]

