2.5 Risk-benefit assessment

2.5.1 Known potential risks

Due to the characteristics of the active ingredients of Humylub Ofteno® PF, particularly its high molecular weight and the fact that it is composed of endogenous substances widely distributed in healthy organisms, the occurrence of serious adverse effects related to the investigational product is not expected. The safety profile of both assets, both individually and in combination, has been described in other studies. See points 2.2.1.3 Safety of sodium hyaluronate, 2.2.2.3 Safety of chondroitin sulfate, and 2.3 Summary of pharmaceutical development of Humylub Ofteno® PF.

As with the rest of the topical ophthalmic application formulations, the possibility of mild and transient burning, SCE and blurred vision is anticipated, with a post-instillation duration of no more than one minute. The procedures involved in the execution of this study, and the medications used for them, are also safe and have been described as part of the complete ophthalmological examination.

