7.4.4.5 Corneal and conjunctival fluorescein staining

A drop of topical anesthetic will be instilled in the bottom of the conjunctival sac, then a second drop will be applied to the tip of the fluorescein strip, allowing it to sit on the strip for 5 seconds to elute the dye, shaking off the excess at the end. A small contact of the strip is made with the conjunctiva at the fundus of the temporal sac, while the patient looks upwards, without damaging the conjunctiva. It will be graded according to the Oxford scale. [48]

The PI will record in the file and the FRCE the grade granted for fluorescein staining of DO and OS, respectively.

Management as AE: corneal stains that are equal to or greater than grade III will be considered as AEs.

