10.1.5 Patients included in the analysis

Those patients who meet an adherence $\geq 65\%$ of the expected weight of the PI and $\geq 80\%$ of expected applications in the patient's diary, will be included in the statistical analysis to meet the objective of the study. If it is not possible to assess the weight of the IP, only the patient's diary will be considered.

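### Staining and hyperemia, treated as safety or tolerability signs in the product's earlier studies, have no planned safety comparison in all exposed patients here

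*Combined protocol and SAP*

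**What the plan says.** **Earlier studies (2.3).** Phase I was done "on the ocular surface of ophthalmologically and clinically healthy subjects", 30 in total over three treatments. Among its safety measures, "epithelial defects in the cornea and conjunctiva, conjunctival hyperemia, and chemosis were considered". On fluorescein, significant "differences were observed at visits 1, 2, and final at the expense of a higher number of grade 0 cases in the comparator group". On the other dye: "For lysmine green staining, a statistically significant difference was observed at visit 2", with no direction given. For hyperemia the only significant difference was at visit 1, where normal values were more frequent on Systane Ultra than on Humylub PF or Xyel. The 2019 phase IV study (326 patients, 90 days) again placed staining under safety: "For the variables defined as primary safety outcomes, such as presence of AEs, TRL, visual acuity and ability, intraocular pressure (IOP), and surface stains" showed no significant between-group difference at any time. It listed hyperemia under tolerability and found no group difference there either.

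**This trial.** Section 7.4.2 lists both dyes and hyperemia as secondary efficacy variables. Section 7.4.3 lists unexpected related adverse events, visual acuity and chemosis as safety. Under 7.4.4.5, "corneal stains that are equal to or greater than grade III will be considered as AEs". Section 7.4.4.7 sets the corresponding level for hyperemia at Efron grade 3.

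**Analysis sets.** Section 10.1.3 gives the safety assessment everyone exposed at least once. Under 10.1.5, patients with at least 65% of expected bottle-weight use and at least 80% of diary applications "will be included in the statistical analysis to meet the objective of the study"; if the bottle cannot be weighed, the diary alone decides.

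**The concern.** A sign that the sponsor twice examined as safety is now examined only as efficacy, and no reason is given. The label matters because it decides which patients are compared. Patients whose eyes look or feel worse may under-use or stop the drops, and the adherence gate then removes them from the only planned between-arm comparison of these grades. Section 3.2 makes non-inferiority in safety a set of objectives (chemosis, adverse events, acuity). A modest excess of low-grade staining or redness could therefore go without a planned safety comparison, although the grades are recorded at every efficacy visit.

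**Working it through.** The plan states no figure on this point that could be reproduced, so the check sets the sections side by side.

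**1. Role of the signs**

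| Study | Staining | Hyperemia | Between-group result |
|---|---|---|---|
| Phase I, 30 healthy subjects | safety | safety | fluorescein differed at visits 1, 2 and final; lissamine at visit 2; hyperemia at visit 1 |
| 2019 phase IV, 326 patients | primary safety | tolerability | no difference in either |
| This trial | secondary efficacy | secondary efficacy | – |

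**2. Routes by which worsening can enter safety here**

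- Listed safety variable (7.4.3): none for staining or hyperemia.
- Automatic adverse event: corneal grade III or more (7.4.4.5, repeated in 7.4.4.6), or Efron grade 3 or more (7.4.4.7). These are absolute levels, not changes from baseline, so a corneal move from grade 0 to II triggers nothing. Section 7.4.4.6 concerns conjunctival lissamine staining, yet its rule is worded for corneal stains. As written, conjunctival staining of any grade has no automatic rule.
- General definition (8.2): it covers worsening of a known condition and has no grade floor, so lesser staining can be reported. Section 7.4.4.1 leaves that to the investigator's judgement.

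**3. Analysis set**

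Section 10.1.5 restricts the analysis for the study objective to adherent patients. It does not name secondary variables, so placing staining and hyperemia in that set is an inference. No other efficacy set is defined, and 10.1.3 keeps the all-exposed set for safety.

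**4. Visibility within the efficacy analysis**

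Section 10.1.2 analyses qualitative variables in 2x2 tables but states no cut-point for the Oxford or Efron grades. Depending on the cut chosen, a one-grade shift may not show.

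**5. Illustration**

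Only the arm size of 60 comes from the plan (10.2.1); the rest is assumed. Suppose 15 of 60 Humylub patients (25.0%) and 6 of 60 comparator patients (10.0%) worsen by one or two grades without reaching an automatic threshold. The difference in all exposed patients is 25.0 − 10.0 = 15.0 points. Let k of the 15 worsened Humylub patients fail the adherence gate, and nobody else. The adherent-set difference is (15 − k)/(60 − k) − 6/60:

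- k = 0: 15/60 = 25.0%, difference 15.0 points
- k = 4: 11/56 = 19.6%, difference 9.6 points
- k = 8: 7/52 = 13.5%, difference 3.5 points

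If instead the 8 non-adherent Humylub patients are unrelated to worsening, the expected number of worsened patients left is 15 × 52/60 = 13. Then 13/52 = 25.0%, and the difference stays at 15.0 points.

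**The case against.** Efficacy placement is legitimate. Staining is a diagnostic sign and one route into the trial (5.1.1), and less staining is a cited benefit of hyaluronate (2.2.1.2). That stands, and the efficacy outcomes should remain.

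Several stronger readings are tempting, and the documents do not support them:

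- *A reader might infer that low-grade staining can never count as harm, or that grade III is the only way in.* Section 8.2 allows any worsening to be reported. It also counts deterioration in a clinical test that relates to symptoms or leads to stopping the study drug. Such events would be analysed in the broad safety population. What remains is that this route is discretionary, in an open-label trial. Section 7.4.3 is limited to unexpected related events, although 3.2 and the table in 7.4.4 refer to adverse events without that limit.
- *A reader might infer that the product causes staining.* Phase I was small and in healthy eyes, and no baseline grades are given. The text counts cases, not eyes, and a direction is stated for fluorescein only, against one unnamed group although there were two comparators. The redness difference was not specific to Humylub PF. The larger study in the target disease, which shared Systane Ultra as a comparator, showed no difference in stains or hyperemia. Neither study used the present comparators.
- *A reader might infer that 2.5.1 conceals the phase I result.* It names only "the possibility of mild and transient burning, SCE and blurred vision is anticipated", but it cross-refers to 2.3, where the result is reported.
- *Table 3 may already cover this.* It appears to cross adverse events with staining, but its layout is broken in the available text, and it names neither a population nor a worsening endpoint.

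Selection by adherence is also a general feature of the plan's efficacy analyses, not peculiar to staining. It is raised here because these signs have a safety history.

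**Conclusion.** The point holds as a low-cost improvement, not as evidence of harm or a flaw that undermines the trial. Worsening of staining or hyperemia below the automatic thresholds has no planned comparison in all exposed patients, and its entry into safety depends on investigator reporting. This rests on reading 10.1.5 as covering the secondary efficacy variables.

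The size cannot be estimated from the documents. The loss from 15 to 3.5 points is an assumed worst case, in which only worsened patients in one arm fail the adherence gate. The loss is zero if adherence and worsening are unrelated.

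**What to change.** Keep change in staining and hyperemia as secondary efficacy outcomes. Add to 7.4.3 and 10.1.3 a safety summary of worsening from baseline in Oxford grade (each dye separately) and in Efron grade, for example by at least one grade in the worse eye. Report it by arm in all exposed patients with any post-dose examination, with a risk difference and 95% interval for Humylub PF against each comparator. State in 10.1.5 which set applies to the secondary variables. Reconcile the corneal-only wording in 7.4.4.6 with that section's conjunctival subject.

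The cost is protocol and SAP wording plus one table, with no new visit or measurement. There are two drawbacks. The same grades appear under both efficacy and safety; section 2.3 shows the 2019 study already did this for tear break-up time. A one-grade cut is also sensitive to grading noise in an open-label trial. The documents offer no basis for that particular cut, so the full grade-shift table should be shown beside it.
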